15. MANAGEMENT OF CORTICOSTEROIDS

Systemic steroids may be decreased at the treating physician's discretion. Non-absorbable oral steroids will be allowed and recorded.

16. PROPHYLAXIS FOR INFECTION

Prophylaxis for infections, including routine monitoring for CMV, EBV will be done per institutional practice. Pre-emptive therapy for CMV will be per institutional practice.

Given the interaction of ibrutinib with azoles, please refer to dose modification section for appropriate dosing guidelines of ibrutinib.

17. USE OF DONOR LYMPHOCYTE INFUSION (DLI)

Use of DLI for mixed chimerism will be at the discretion of the treating physician. Ibrutinib will be held for at least 7 days prior to DLI and resumed at least after 14 days post DLI. Anticipated planned donor lymphocyte infusion in the first 3 months post-HCT is an exclusion criterion.

18. EFFICACY MEASUREMENT

- 18.1** A review committee led by [name], MS (Vanderbilt University) will review all response assessments. Cases requiring review of imaging studies will be done in coordination by [name] and a radiologist from the individual centers.
- 18.2** The primary endpoint is to study the use of ibrutinib starting between days 60 to day 90 after allogeneic HCT until 12 months post HCT to improve the PFS at 12 months post HCT by 25% compared to historical controls in patients with MCL and CLL.
- 18.3** The following established definitions of relapse, recurrence and responses will be used for CLL.⁵²

18.3.1 Progressive Disease is Defined if One of the Criteria is Documented[€]:

- The appearance of a new enlarged node >1.5 cm, splenomegaly or hepatomegaly *
- An increase of 50% or more in size if a previously involved site (lymph node, spleen or liver)^

- Richter's transformation documented by lymph node biopsy
- Development of neutropenia, anemia or thrombocytopenia attributable to CLL§
- € The iwCLL definition of PD defined as an increase of 50% or more in the total circulating lymphocyte count with absolute lymphocyte count of $>5000/\mu\text{l}$ or greater has been deleted as patients are to receive the B-cell receptor kinase inhibitor
- * Post allogeneic stem cell transplantation, patients may develop adenopathy that can be attributable to other causes (infections, inflammatory state). Adenopathy should be attributable to CLL by the investigator.^
- ^ A lymph node that was 1 to 1.5 cm previously must increase by 50% or more to a size greater than 1.5 to 2.0 cm in the longest axis
- § Cytopenias cannot be used to determine disease progression in the presence of other immunosuppressive therapies. The cytopenias are defined as a decrease in hemoglobin level by more than 2 g/dl (20g/L) or to less than 10 g/dl (100g/L) or a decrease in platelet count to less than $100,000/\mu\text{l}$ ($100 \times 10^9/\text{L}$) in the presence of clonal CLL infiltrates on the bone marrow biopsy.

18.3.2 Complete Remission Requires All of the Following Criteria:

- Absolute lymphocyte count $<4000/\text{microL}$ ($4 \times 10^9/\text{L}$).
 - No lymph nodes >1.5 cm in diameter.
 - No hepatomegaly or splenomegaly.
 - No constitutional symptoms attributable to CLL.*
 - Bone marrow recovery as demonstrated by ANC $>1500/\text{microL}$ ($1.5 \times 10^9/\text{L}$), platelet count $>100,000/\text{microL}$ ($100 \times 10^9/\text{L}$), and hemoglobin concentration >11 g/dL (110 g/L) in the absence of transfusion or growth factor support.
 - Bone marrow free of clonal CLL cells by conventional flow cytometry and/or immunohistochemistry and without nodular lymphoid aggregates.
- * Constitutional symptoms include $\geq 10\%$ unintentional weight loss within the previous six months, fatigue that interferes with work or usual activities, fevers greater than 100.5°F ($>38^\circ\text{C}$) for ≥ 2 weeks, or night sweats for >1 month. Note that in our trial, patients are post allogeneic stem cell transplantation and may have these symptoms that are not a result of CLL but attributable as a primary or secondary cause related to allogeneic stem cell transplant. The cause of these symptoms should be documented by the investigator.

18.3.3. Partial Remission: At Least One of These Criteria Must be Documented:

- A decrease in the peripheral absolute lymphocyte count by at least 50% from the level prior to therapy.
- A reduction in previously enlarged nodes by at least 50% with no increase in the size of any single lymph node and no new enlarged lymph nodes. An increase of <25% in a lymph node <2 cm is not considered significant.
- If enlarged prior to therapy, the liver and spleen should be reduced in size by at least 50%.

One of the following hematologic parameters must be met in addition to one of the above criteria in order to qualify for a PR:

- ANC $\geq 1500/\mu\text{L}$ ($1.5 \times 10^9/\text{L}$) or greater than 50% improvement over baseline (if this value was abnormally low at baseline) without granulocyte colony-stimulating factor support.
- Platelet count $\geq 100,000/\mu\text{L}$ ($100 \times 10^9/\text{L}$) or at least 50% improvement over baseline (if this value was abnormally low at baseline).
- Hemoglobin concentration $\geq 11 \text{ g/dL}$ (110 g/L) or 50% improvement over baseline (if this value was abnormally low at baseline) without red blood cell transfusions or erythropoietin support.

Note: Partial remission with Lymphocytosis: PR criteria with the exception of ALC are met is consistent with a PR with lymphocytosis.

18.3.4 Nodular Partial Remission:

Persistent bone marrow nodules on bone marrow biopsy in patients achieving a CR or PR. Lymphoid aggregates should be evaluated with immunohistochemistry to determine whether they are comprised of CLL cells, lymphocytes other than CLL cells, or T cells.

18.3.5 Stable Disease:

Patients, who do not meet the criteria for a complete remission, partial remission, or progressive disease, have stable disease. Stable disease is therapeutically equivalent to a nonresponse (i.e., refractory disease).

18.4 The Following Established Definitions of Relapse, Recurrence and Responses Will Be Used for MCL and FL

18.4.1 Progressive disease or relapse is defined if one of the criteria is documented (either PET/CT or CT can be used).

PET-Based Response:

- Progressive metabolic disease
- Score of 4 or 5 (on a 5-point scale) with an increase in intensity of uptake from baseline and /or
- New FDG-avid foci consistent with lymphoma rather than another etiology (infection, inflammation). If uncertain regarding etiology of new lesions, biopsy or interval scan may be considered.

CT-Based Response:

- An individual node/lesion must be abnormal with an LDi > 1.5 cm and Increase by $\geq 50\%$ from PPD nadir and an increase in LDi or SDi from nadir (0.5 cm for lesions ≤ 2 cm, 1.0 cm for lesions > 2 cm)
 - In the setting of splenomegaly, the splenic length must increase by > 50% of the extent of its prior increase beyond baseline (for e.g., a 16-cm spleen must increase to > 17.5 cm). If no prior splenomegaly, must increase by at least 2 cm from baseline[¥]
 - New or recurrent splenomegaly
 - New or clear progression of preexisting non-measured lesions
 - A new node >1.5 cm in any axis
 - A new extranodal site >1.0 cm in any axis; if <1.0 cm in any axis its presence must be unequivocal and must be attributed to lymphoma.
 - Assessable disease of any size unequivocally attributable to lymphoma
 - New or recurrent Bone marrow involvement
- ¥ Spleen size baseline 13 cm in vertical length

LDi: longest transverse diameter of a lesion; SDi: Shortest axis perpendicular to LDi; PPD: cross product of LDi and SDi.

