3. PRIMARY OBJECTIVE

To study the use of ibrutinib starting between day 60 and day 90 after allogeneic HCT until 12 months post HCT to improve the PFS at 12 months post HCT by 25% compared to historical controls. The sample size is designed to address this primary endpoint.

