21. SUBJECT WITHDRAWAL

21.1 Withdrawal from Study Treatment

Study treatment will be withdrawn if:

- Patient experiences relapse or progression of underlying disease while on ibrutinib, and further continuation is not felt to be beneficial.
- Unacceptable toxicity: an intercurrent illness or adverse event that prevents further ibrutinib administration for more than 28 continuous days
- Non-compliance with taking ibrutinib or with following protocol
- Investigator decision
- Withdrawal of consent for treatment by subject
- Subject becomes pregnant
- Study termination by sponsor-investigator

All subjects, regardless of discontinuation of study treatment will undergo end of study visit and be followed for progression and survival until 2 y post HCT by imaging (CT scan and/or PET scan or other imaging) or other modalities per the discretion of the treating physician.

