24. STATISTICAL ANALYSES PLAN

24.1 Analysis Plan

The statistical analysis plan will address the primary aim: To study the use of ibrutinib starting between day 60 and day 90 after allogeneic HCT until 12 months post HCT to improve the PFS at 12 months post HCT by 25% compared to historical controls. This will be restricted to cohort A which includes the diagnoses of CLL and MCL, only.

- PFS is defined as time to progression, or relapse of the underlying disease for which transplant was undertaken, or death from any non-relapse causes, starting from the date of stem cell transplant (SCT).
- We will estimate the 12-month PFS rate with a 95% confidence interval using the method of Kaplan-Meier and using the Greenwood variance estimator, and we will compare this estimate with the rate in the historical controls.
- Historical data
 - In a study by Sobecks et al⁵³, the outcomes of patients with CLL after ablative (n=163) and reduced intensity conditioning (RIC) 134 were reported. Outcomes were stratified based on when the HCT occurred (< 2000, or ≥ 2000). We expect the majority of patients with CLL on the proposed study to be undergoing RIC allo HCT, thus relevant data (≥ 2000 and RIC allo HCT) are taken into account for sample size analyses. One year PFS was 62% (95% CI 51-72).
 - In a study by Urbano-Ispizua et al⁵⁴, the outcomes of patients with MCL undergoing ablative (n=149) and RIC (n=351) allo-HCT was reported. The 1y PFS for patients with MCL (personal communication, CIBMTR) was 52% (95% CI 47-56)
- The proportion of patients with CLL and MCL enrolling in this study will not be known at the start of the study or be controlled for during the accrual period. Thus, we studied the impact on power of varying proportions of these two diagnoses on outcome for a given effect size.
- We will compare our overall PFS rate with the weighted average of the historical rates in CLL and MCL, using the proportion of our sample with each of these two diagnoses as the weights.

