APPENDIX 2:

Disease status assessment: Pre HCT: CLL. CIBMTR form 2013, Revision 2.0, 10 pages.

Form 2013 R2.0: Chronic Lymphocytic Leukemia(CLL) Pre-HSCT Data

Center:

CRID:

Autoimmune disorder(s) at diagnosis:

8 Immune hemolytic anemia

yes no Unknown

10 Immune thrombocytopenia

yes no Unknown

11 Positive Coombs' test

yes no Unknown

12 Other

yes no Unknown

13 Specify other autoimmune disorder: _____

14 What was the Rai stage at diagnosis?

- low risk - stage 0 - lymphocytosis ($>15,000 \times 10^9/L$) in blood or bone marrow only
- intermediate risk - stage I - lymphocytosis plus enlarged lymph nodes (lymphadenopathy)
- intermediate risk - stage II - lymphocytosis plus enlarged liver or spleen with or without lymphadenopathy
- high risk - stage III - lymphocytosis plus anemia (Hgb < 11 g/dL) with or without enlarged liver, spleen, or lymph nodes
- high risk - IV - lymphocytosis plus thrombocytopenia (platelet count $< 100 \times 10^9/L$) with or without anemia or enlarged liver, spleen, or lymph nodes
- Unknown

16 What was the Binet stage at diagnosis? (Five lymphoid bearing areas are possible: axillary, cervical, inguino-femoral, liver, and spleen.)

- stage A - two or fewer lymphoid bearing areas enlarged, without anemia or thrombocytopenia
- stage B - three or more lymphoid bearing areas enlarged, without anemia or thrombocytopenia
- stage C - presence of anemia (Hgb < 10.0 g/dL) or thrombocytopenia (platelet count $< 100 \times 10^9/L$)
- Unknown

18 What were the disease symptoms at diagnosis?

- A - none of the symptoms listed in B below
- B - unexplained weight loss of $>10\%$ of body weight in six months before treatment; unexplained fever $> 38^\circ C$; or, night sweats
- Unknown

17 Was there extramedullary and/or extranodal involvement at diagnosis?

yes no Unknown

Specify site(s) of involvement:

18 Central nervous system (CNS)

yes no

19 Liver

yes no

20 Lung

yes no

21 Spleen

yes no

Form 2013 R2.0: Chronic Lymphocytic Leukemia(CLL) Pre-HSCT Data

Center:

CRID:

22 Specify centimeters below costal margin: _____

23 Other site:

yes no

24 Specify: _____

If the recipient is 18 years of age or older, complete the Karnofsky Scale. If the recipient is younger than 18 years of age, complete the Lansky Scale.

25 Enter age-appropriate Karnofsky or Lansky score at diagnosis: _____

Laboratory Studies at Diagnosis

Questions: 26 - 80

26 Lymphocytes in bone marrow:

Known Not known

27 _____ %

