148 Lower limit of normal for IgG: _____

149 IgA: Known Not known

150 _____ mg/dL g/dL g/L

161 Lower limit of normal for IgA: _____

162 IgM: Known Not known

163 _____ mg/dL g/dL g/L

164 Lower limit of normal for IgM: _____

165 Was molecular testing/immunophenotyping performed at the time of disease assessment prior to the preparative regimen?
 yes no

Specify the testing method(s) used:

166 Immunophenotyping (4 color flow cytometry)
 yes no

167 Specify the date immunophenotyping was performed: ____-____-____

168 Was disease detected?
 yes no

169 Heavy chain gene rearrangement (A2O-PCR)
 yes no

170 Specify the date the heavy chain gene rearrangement testing was performed: ____-____-____

181 Was disease detected?
 yes no

Disease Status at the Last Assessment Prior to the Preparative Regimen Questions: 182 - 184

182 What was the disease status at the last evaluation prior to the preparative regimen?

- complete response (CR) - no lymphadenopathy; no organomegaly; neutrophils > 1.5 x 10⁹/L; platelets > 100 x 10⁹/L; hemoglobin > 11g/dL; lymphocytes < 4 x 10⁹/L; bone marrow < 30% lymphocytes; absence of constitutional symptoms
- nodular partial response (NPR) - complete response with persistent lymphoid nodules in bone marrow
- partial response (PR) - ≥50% decrease in peripheral blood lymphocyte count from pretreatment value; ≥50% reduction in lymphadenopathy if present pretreatment; ≥50% reduction in liver and spleen size if enlarged pretreatment; one or more of the following: neutrophils ≥ 1.5 x 10⁹/L or 50% improvement over baseline, platelets > 100 x 10⁹/L or 50 % improvement over baseline, hemoglobin > 11.0 g/dL or 50% improvement over baseline
- stable disease (SD) - no change; not complete response; partial response; nor progressive disease
- progressive disease (Prog) - one or more of the following: ≥50% increase in the sum of the products of ≥ 2 lymph nodes (≥ 1 node must be ≥ 2 cm) or new nodes; ≥ 50% increase in liver or spleen size, or new hepatomegaly or splenomegaly; ≥ 50% increase in absolute lymphocyte count to ≥ 5 x 10⁹/L; transformation to a more aggressive histology
- untreated - no chemotherapy given in the 6 months prior to HSCT
- Not assessed

183 Date of most recent assessment for disease status prior to the preparative regimen: ____-____-____

First Name: _____ Last Name: _____

Phone number: _____ Fax number: _____

184 E-mail address: _____

CIBMTR Form 2013 revision 2.0 last updated July 2007

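### The lymphocyte-count criterion for CLL progression is dropped with no on-drug limit, so a blood- or marrow-only CLL relapse off ibrutinib may not count as a PFS event

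*Combined protocol and SAP*

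**What the plan says.** Section 18.3.1 lists what counts as CLL progression: new or enlarging nodes, spleen or liver; Richter's transformation on biopsy; and cytopenia attributable to CLL. A footnote says that the iwCLL lymphocyte-count criterion (a rise of 50% or more, with a count above 5000/µl) "has been deleted as patients are to receive the B-cell receptor kinase inhibitor". A second footnote narrows the cytopenia route: "Cytopenias cannot be used to determine disease progression in the presence of other immunosuppressive therapies".

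Section 24.1 times PFS from the transplant date and counts progression, relapse or non-relapse death. Section 3 gives the drug period as "starting between day 60 and day 90 after allogeneic HCT until 12 months post HCT". Section 21.1 says that all subjects, whatever happens to treatment, will "be followed for progression and survival until 2 y post HCT by imaging" or other modalities. Section 20 asks for an end-of-study visit even for patients who never start ibrutinib.

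The primary comparison in Section 24.1 sets cohort A's PFS against a weighted average of historical one-year rates: 62% for CLL and 52% for MCL. No progression definition is given for either.

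**The concern.** The reason given for the deletion is exposure to the drug, and it is a fair reason while a patient takes it. The deletion itself is not tied to exposure. It applies over all of PFS time, including stretches with no ibrutinib.

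Off drug, the remaining criteria leave a gap for disease that returns only in blood or marrow. If such a relapse is not an event, or becomes one later, the 12-month PFS estimate is too high. In a single-arm trial judged against a fixed historical rate, a difference in event definition passes straight into the primary result.

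**Working it through.** **1. The plan's own figures reproduce, so the power arithmetic is not at issue.** With CLL share w, the historical rate is w × 0.62 + (1 − w) × 0.52, which gives 0.55 at w = 0.30 and 0.59 at w = 0.70, as in Section 24.2. For power I used the exponential test on the cube-root scale: φ = λ^(1/3) with λ = −ln(one-year PFS), SE = φ/(3√Q), Q = 65 × the mean event probability with follow-up uniform on 2 to 4 years, two-sided 0.05, SE taken at the alternative. The 25% rows come out at 91.7, 92.9, 94.3, 95.3 and 96.4%, against 91, 92, 93, 95 and 96% in the plan. All 15 cells agree within 1.4 points.

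**2. Where the deletion applies and where its reason applies.**

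| Period within PFS time | On ibrutinib? | Does the stated reason apply? |
|---|---|---|
| Transplant to first dose (day 60-90) | No | No |
| Patients who never start | No | No |
| First dose to month 12, taking drug | Yes | Yes |
| After early permanent stop | No | No |

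Early stopping is not rare in the protocol's own safety summary (Section 6.3.3): 16.8% of patients with hematologic malignancy and 42.9% of patients with chronic GVHD stopped because of an adverse event. Section 24.1 does not name the analysis set, so how far never-starters enter the estimate is not stated.

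**3. Routes left for a blood- or marrow-only CLL relapse off drug.**
- Lymphocyte count: deleted.
- Cytopenia: barred during other immunosuppression. Section 5.3 starts the taper at day 100 and aims to stop by 6 months; Section 5.4 says day 180 to 270.
- Marrow: Section 18.4.1 lists new or recurrent marrow involvement as progression for MCL and FL. Section 18.3.1 has no such item for CLL, although Section 20 schedules a marrow biopsy between day 30 and day 60.
- Default: under Section 18.3.5, a patient who meets neither remission nor progression criteria has stable disease. Complete remission (18.3.2) requires a lymphocyte count below 4000/µl and a marrow free of clonal cells. A patient can thus lose remission in blood and marrow without having an event.

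**4. Possible size (assumptions, not document figures).** The historical CLL failure rate at one year is 100 − 62 = 38%. Assume that half are progressions: 0.5 × 38 = 19 points. Assume that 10 to 30% of those show first by lymphocyte count alone: 1.9 to 5.7 points of CLL PFS. Scaled by CLL share:
- lowest: 0.19 × 0.10 × 0.30 = 0.6 points of overall PFS;
- highest: 0.19 × 0.30 × 0.70 = 4.0 points.

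The planned gain is 0.25 × 0.55 = 13.8 to 0.25 × 0.59 = 14.8 points. The 0.6 to 4.0 points cover on-drug as well as off-drug cases and treat none as becoming an event by month 12. The off-drug part is smaller, and the documents do not allow it to be separated.

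**5. Effect on the test, only if the benchmark counted lymphocytosis.** Suppose no true effect and a definitional shift of d points in CLL PFS, so that observed PFS is p₀ + w·d. The chance of a false finding in favour of ibrutinib, nominally 2.5%, becomes:

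| d in CLL | Method | CLL 30% | CLL 50% | CLL 70% |
|---|---|---|---|---|
| 2 points | Exponential test (Section 24.2) | 3.4% | 4.2% | 5.1% |
| 2 points | 12-month Kaplan-Meier, normal approximation | 3.1% | 3.6% | 4.2% |
| 5 points | Exponential test | 5.2% | 8.3% | 12.7% |
| 5 points | 12-month Kaplan-Meier | 4.3% | 6.1% | 8.4% |

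The Kaplan-Meier rows use Φ((p − p₀)/√(p(1 − p)/65) − 1.96) with complete follow-up to month 12. For example, at CLL 50% and d = 5, p₀ = 0.57 and p = 0.595, giving Φ(0.025/0.0609 − 1.96) = 6.1%. If the benchmark did not count lymphocytosis, d = 0 and the rate stays at 2.5%.

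**The case against.** A reader might infer that the trial scores CLL more leniently than its benchmark, because the registry form in Appendix 2 counts an "increase in absolute lymphocyte count to ≥ 5 x 10⁹/L" as progression. The documents do not support that step. The appendix is titled "Disease status assessment: Pre HCT: CLL. CIBMTR form 2013, Revision 2.0, 10 pages": it records response to earlier lines of therapy and status before the preparative regimen, not outcome after transplant. The 62% CLL rate comes from a cited transplant study whose progression definition is not given. The registry is named as source only for the MCL rate, to which a CLL lymphocyte count does not apply. A bias toward ibrutinib is therefore possible, not shown.

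The gap is also narrower than it first looks. Once immunosuppression has stopped, cytopenia with clonal marrow infiltrates can count. Richter's transformation always counts. PFS includes relapse as well as progression, suspected relapse typically goes to histology (Section 7.2), and a committee reviews all response assessments (Section 18.1). MCL patients are unaffected, and months 12 to 24 do not enter the 12-month Kaplan-Meier estimate.

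These points limit the size but do not close the gap. Section 18.3 gives CLL no relapse definition beyond the progression list, so a committee that follows the text has no criterion to apply to a blood- or marrow-only relapse. A bare lymphocyte-count rule off drug would be a poor remedy, since lymphocytes can rise after transplant for reasons other than CLL. The deletion on drug has a stated reason and is not disputed.

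**Conclusion.** The point holds as a gap in the primary endpoint definition. The deletion reaches time to which its reason does not apply, and in that time a blood- or marrow-only CLL relapse may pass as stable disease. Twelve-month PFS may then be overstated.

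The size is unknown from the documents. The 0.6 to 4.0 points of overall PFS rest on two assumptions (half of CLL failures are progressions; 10 to 30% of those are lymphocytosis-only at first) and form an upper range for the off-drug problem. Bias in the historical comparison is conditional: toward ibrutinib if the 62% rate counted lymphocytosis, zero from this source if it did not. The power table is not affected. This is a cheap improvement, not a flaw that invalidates the design.

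**What to change.** - In Section 18.3.1, limit the deletion to time on ibrutinib. Off ibrutinib (transplant to first dose, never started, after permanent stop), count a lymphocyte rise that meets the iwCLL threshold as progression only when it is confirmed as clonal CLL by IGH sequencing or flow cytometry and attributed to CLL.
- Pre-specify in Section 24.1 a PFS sensitivity analysis that counts confirmed clonal lymphocytosis throughout, on and off drug.
- State the progression definition behind the 62% CLL rate, or state that it is unknown, so that readers can judge which version of PFS is like for like.

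Cost: wording in Sections 18 and 24, and one added data item. The listed hematology minimum in Section 20 has white cells and neutrophils but no absolute lymphocyte count, although complete remission already needs it. The cohort A table in Section 22.1 schedules no hematology between the preparative regimen and day 60, so counts for that window must come from routine care. IGH sequencing samples are already planned before transplant, before ibrutinib, at months 6, 9 and 12, and at suspected relapse; CD19 subsets alone do not show clonality. The PFS estimate may be slightly lower.

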4. SECONDARY AND EXPLORATORY OBJECTIVES

- CLL/MCL cohort (Cohort A)
 - To increase the incidence of successful outcome (defined as lack of requirement of second line therapy for acute GVHD, lack of NIH severe chronic GVHD, lack of progression or relapse of CLL/MCL, lack of death from disease or non-relapse causes) to at least 60% at 1 year post HCT.

- To study the safety and tolerability of ibrutinib post HCT in patients with non-Hodgkin lymphoma (NHL) and HL (cohort A and B combined)
- Acute GVHD
 - To study the incidence of grade 3-4 acute GVHD in the first 6 months post HCT in patients with NHL and HL (cohort A and B combined)
 - To study the incidence of second line therapy (systemic only) for acute GVHD in the first 6 months post HCT in patients with NHL and HL (cohort A and B combined)
 - To study the incidence of recurrent acute GVHD in the first 6 months post HCT in patients with NHL and HL (cohort A and B combined)
- Chronic GVHD
 - To study the incidence and severity of chronic GVHD in the first 12 months post HCT in patients with NHL and HL (cohort A and B combined)
 - To study the incidence of lung involvement with GVHD in the first 12 months post HCT in patients with NHL and HL (cohort A and B combined)
 - To study the incidence of sclerotic skin chronic GVHD in the first 12 months post HCT in patients with NHL and HL (cohort A and B combined)
- To study the incidence of infectious deaths not related to GVHD in patients with non-Hodgkin and Hodgkin lymphoma (cohort A and B combined)
- Correlative studies
 - Cohort A: To study the association of MRD as detected by IgH sequencing prior to starting ibrutinib and compare to post ibrutinib at month 6, 9 and 12 after HCT. In addition to study the impact of onset of new acute or chronic GVHD on MRD.
 - Cohort A: To study the association of T-cell clonality by T cell receptor (TCR) Vb sequencing prior to starting ibrutinib and compare to post ibrutinib at month 6, 9 and 12 after HCT. In addition to study the impact of onset of new acute or chronic GVHD on TCR sequencing.
 - Cohort A: To study the association of B cell receptor signaling pathways and immune function with response by single cell mass cytometry prior to starting ibrutinib and compare to post ibrutinib at month 6, 9 and 12 after HCT.
 - Cohort A: To study the association of single cell mass cytometry that investigates B cell receptor signaling and its association with new acute or chronic GVHD on BCR signaling.

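### CLL partial remission in Section 18.3.3 needs only one disease criterion plus one blood count, so it can be met while existing nodes grow, and no rule ranks PD above PR

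*Combined protocol and SAP*

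**What the plan says.** Section 18.3.3 defines CLL partial remission in two layers. The first is a list of three disease criteria under the rule "At Least One of These Criteria Must be Documented":

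- Lymphocytes: "A decrease in the peripheral absolute lymphocyte count by at least 50% from the level prior to therapy".
- Nodes: "A reduction in previously enlarged nodes by at least 50% with no increase in the size of any single lymph node", and no new enlarged nodes.
- Liver and spleen: halved in size, if enlarged before therapy.

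The second layer is a blood-count condition on ANC, platelets or hemoglobin: "One of the following hematologic parameters must be met in addition to one of the above criteria in order to qualify for a PR". That sentence repeats the one-of rule, so the wording in the heading of the subsection is not a stray slip.

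A closing note adds that "PR criteria with the exception of ALC are met is consistent with a PR with lymphocytosis".

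Section 18.3.1 makes either of these progressive disease, among other criteria: "An increase of 50% or more in size if a previously involved site", or a new node over 1.5 cm, which must be attributed to CLL. Section 18.3.5 defines stable disease as whatever is not CR, PR or PD, and equates it with non-response. Section 18.1 has a committee review all response assessments.

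**The concern.** A partial remission should mean that the disease has shrunk wherever it was measurable. Under a one-of rule it need shrink in only one compartment. The lymphocyte criterion carries no nodal condition, so it can supply the whole disease side of a PR on its own, and the patient's nodes may be stable or growing.

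Because stable disease is defined by exclusion, every PR granted this way leaves the non-response group. Where response is later related to a biomarker, some patients without nodal response would be counted among the responders. Cohort A has one exploratory objective of that kind: "To study the association of B cell receptor signaling pathways and immune function with response by single cell mass cytometry".

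A second gap is that PR and PD can both be satisfied at the same visit, and Section 18.3 does not say which is recorded.

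**Working it through.** The plan gives no figure to reproduce here, so the check is of the logic.

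**1. The rule as written.** Let A, N and O stand for the lymphocyte, nodal and liver/spleen criteria, and H for at least one blood-count parameter.

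- As written: PR = (A or N or O) and H.
- With all disease criteria required: PR = A and N and O and H.

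Four yes/no items give 2⁴ = 16 patterns. As written, (2³ − 1) × 1 = 7 of the 16 are PR; with all required, 1 of 16 is. This counts patterns, which are not equally likely, so it is not a rate of misclassification.

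**2. One patient run through both definitions.** The values are assumptions for illustration: lymphocytes fall from 6,000 to 2,900/µL, platelets are 120,000/µL, one node measures 2.0 cm at baseline, there is no new node, and liver and spleen were never enlarged.

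- A: (2,900 − 6,000) / 6,000 = −51.7%, so A is met.
- H: 120,000 is at least 100,000, so H is met.
- N: the node has not halved, so N is not met.

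| Node now (cm) | Change | PR as written | PD (18.3.1) | PR if all applicable criteria required |
|---|---|---|---|---|
| 2.0 | 0% | yes | no | no |
| 2.4 | +20% | yes | no | no |
| 2.8 | +40% | yes | no | no |
| 2.9 | +45% | yes | no | no |
| 3.0 | +50% | yes | yes | no |
| 3.2 | +60% | yes | yes | no |

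The same overlap arises if the 2.0 cm node is unchanged but a new node over 1.5 cm appears and is attributed to CLL: A and H still give PR, and the new node gives PD.

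**3. How much the blood-count condition screens out.** Platelets of 100,000/µL satisfy it. Section 9, item 11 sets the same platelet threshold for starting ibrutinib (50,000 if the marrow is involved). A patient who starts under the general threshold already meets this condition on that day.

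**4. Other text on the same question.**

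- The lymphocytosis note treats the lymphocyte count as one member of a set whose other members are met. Under a one-of rule, a patient with halved nodes and an adequate blood count is already a PR whatever the lymphocyte count, so the note adds only a label.
- Form 2013 in Appendix 2 lists the lymphocyte reduction together with "≥50% reduction in lymphadenopathy if present pretreatment; ≥50% reduction in liver and spleen size if enlarged pretreatment", and applies its one-or-more wording only to the blood counts.
- A footnote in Section 18.3.1 removes the lymphocyte rise from the PD criteria because patients receive a B-cell receptor kinase inhibitor. Section 18.3.3 still lets a lymphocyte fall carry the disease side of PR alone.

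**5. Where PR enters an analysis.** PFS in Section 24.1 uses progression, relapse and death. The composite in Sections 4 and 5.4 uses progression or relapse, second-line therapy for acute GVHD, severe chronic GVHD and death. Neither uses PR. Section 4 names response in the objective quoted above without defining it. The mass cytometry text under Section 7.3 groups patients by CR and by relapse or progression. Section 24.4 names no response variable.

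**6. The pool.** The power table in Section 24.2 runs from 30% to 70% CLL in 65 patients: 65 × 0.30 = 19.5 and 65 × 0.70 = 45.5, or about 20 to 46 patients. This is how many would be classified under Section 18.3.3 in those scenarios. How many would be misclassified is not given.

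**The case against.** The strongest reply is that little in the plan depends on CLL partial remission. The primary and composite endpoints ignore it, the described mass cytometry groups are CR and relapse or progression, and CR is strict because all its criteria must be met. A committee sees every assessment. Node growth is capped by the PD rule, and since one PD criterion is enough, such a patient is a PFS event whatever Section 18.3.3 says. The lymphocytosis note can also be read as a label for a PR reached through nodes or organs, so it is awkward rather than contradictory.

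Most of this stands, and it limits the point. It does not remove it. A committee applies the written definition, and Section 18.3 is the only on-study CLL response definition in the protocol. The cap still leaves growth of up to just under 50% inside PR. The PD reading is reasonable, but it is not stated as a precedence rule.

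A reader might infer more than the documents support:

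- *That a halved lymphocyte count alone makes a PR.* It does not; a blood-count parameter is also mandatory.
- *That the response variable in the correlative objective is wrong.* It is undefined, so this cannot be shown.
- *That one patient could be PR in the trial and stable on the registry form at the same visit.* Form 2013 collects pre-transplant data, covering earlier lines of therapy and status before conditioning. Section 20 uses it at screening and allows direct database entry instead. It shows two differing definitions, applied at different times.
- *That conditioning makes most patients meet the lymphocyte criterion.* No figure supports this, and it depends on what the text means by the level before therapy. If that is the level before ibrutinib, any fall due to conditioning is already in the baseline.
- *That hardly any non-responders would remain for comparison.* This needs invented rates of stable disease and lymphocyte fall, and it leaves out progressors. The historical one-year CLL PFS of 62% in Section 24.1 implies that 100 − 62 = 38% progress, relapse or die by then.

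**Conclusion.** The point holds as a defect in a response definition. As written, a CLL patient can be a PR on a halved lymphocyte count plus one blood count while existing nodes grow by up to just under 50%. Beyond that limit, or with a new CLL node over 1.5 cm, PR and PD coincide with no stated precedence. The rule also fits poorly with the section's own lymphocytosis note and differs from the Appendix 2 definition.

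The consequence is confined to places where Section 18.3.3 supplies response. CLL responders and stable patients may then be misclassified, which bears on the exploratory cohort A objective if its response variable includes PR. The primary PFS analysis and its power do not use PR; PFS could be touched only indirectly, if a patient meeting both definitions were recorded as PR. The size of the effect cannot be derived from the documents. Whether the wording departs from the published CLL criteria cited in Section 18.3 cannot be checked here either. The change should be made, but the primary result does not depend on it.

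**What to change.** Reword Section 18.3.3 and the correlative plan as follows:

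- Require every one of the lymphocyte, nodal and liver/spleen criteria that was abnormal at baseline, plus one blood-count parameter.
- Name that baseline: before conditioning or before ibrutinib.
- Waive only the lymphocyte criterion for PR with lymphocytosis, so that the note has a clear meaning.
- State that PD overrides PR when both are met.
- In Section 4 or 24.4, say which response categories the correlative analysis uses (for example CR alone, or CR and PR together) and how stable disease is counted.

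The cost is small. No new assessments or data are needed, and the sample size is unaffected. Fewer patients will be called PR and more will be called stable. Any CLL assessments already classified under the present wording would need to be reclassified from data already collected.
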